ICH-GCP E6 can be accessed by copying and pasting this URL into your browser: <http://www.fda.gov/downloads/Drugs/Guidances/ucm073122.pdf>

Table of Contents

1. Objectives	4
2. Background	4
3. Study Design	5
4. Inclusion and Exclusion Criteria	5
5. Number of Subjects	6
6. Study Timelines	6
7. Study Endpoints	6
8. Research Setting	7
9. Resources Available	7
10. Prior Approvals	7
11. Multi-Site Research	8
12. Study Procedures	8
13. Data Analysis	8
14. Provisions to Monitor the Data to Ensure the Safety of Subjects	9
15. Withdrawal of Subjects	9
16. Data Management/Confidentiality	9
17. Data and Specimen Banking	11
18. Risks to Subjects	11
19. Potential Benefits to Subjects	11
20. Recruitment Methods	12
21. Provisions to Protect the Privacy Interests of Subjects	12
22. Economic Burden to Subjects	12
23. Compensation	13
24. Compensation for Research-Related Injury	13
25. Consent Process	14
26. Documentation of Consent	16
27. Study Test Results/Incidental Findings	17
28. Sharing Study Progress or Results with Subjects	18
29. Inclusion of Vulnerable Populations	18
30. Community-Based Participatory Research	19
31. Research Involving American Indian/Native Populations	19
32. Transnational Research	19
33. Drugs or Devices	19
Checklist Section	20

1. Objectives

1.1. *The overall objective is to validate the methodology of a metaplasticity experimental design by assessing change in motor excitability after administration of priming transcranial direct current stimulation (tDCS) followed by repetitive transcranial magnetic stimulation (rTMS) in healthy human participants. Our primary objective is to compare pre- and post-measures of cortical excitability before priming tDCS (anodal, cathodal or sham) [M1], directly after priming tDCS [M2], directly after inhibitory rTMS [M3], and 10 minutes after inhibitory rTMS [M4]. Our secondary objective is to evaluate the sensitivity of motor excitability outcome measures response to the noninvasive neurostimulation (e.g. rTMS and tDCS). Our future direction is to apply this validated protocol in patient populations to better understand how disease states affect metaplasticity.*

1.2. *Aim 1: To compare pre- and post- measures of cortical excitability after inhibitory and excitatory priming of the motor cortex. Hypothesis 1: We expect priming tDCS to affect the response to rTMS, namely we expect “inhibitory” cathodal tDCS to cause a reversal of the normal inhibitory effect of 1Hz rTMS. Hypothesis 2: We expect “excitatory” anodal tDCS to have no effect on the normal inhibitory effect of 1Hz rTMS. Hypothesis 3: We expect sham tDCS to have no effect on the normal inhibitory effect of 1Hz rTMS.*

Exploratory Aim 2: To evaluate the sensitivity of motor outcome measures to changes in cortical plasticity. Hypothesis 1: We expect different measures of motor cortex excitability to be more sensitive than others at detecting changes in cortical excitability. We will be comparing in an exploratory but systematic fashion various measures of motor cortex excitability (e.g. peak-to-peak amplitude change in motor evoked potential (MEP), the integrated area of the MEP (root mean square), the cortical silent period (CSP)), and behavioral measures (reaction time).

2. Background

2.1. *rTMS and tDCS are relatively new modalities that have shown promise in the evaluation and treatment in a variety of neurologic and psychiatric disorders as well as understanding normal brain processes in the healthy human brain. One specific area of interest has been the concept of metaplasticity in the motor cortex in healthy brains and how this is modified in the disease state. Metaplasticity refers to changes in synaptic efficacy such as long-term potentiation (LTP) and long-term depression (LTD), which can be influenced by prior neuronal activity. In humans, we can study these LTP-like and LTD-like changes using non-invasive neurostimulation (e.g. tDCS and rTMS).*

2.2. *Previous studies (Siebner et al. 2004) have shown that preconditioning with anodal (“excitatory”) tDCS followed by inhibitory rTMS led to a period in which corticospinal excitability was reduced below baseline. Conversely, preconditioning with cathodal tDCS followed by 1Hz rTMS caused a resulting*

PROTOCOL TITLE: *Metaplasticity in the human motor cortex: validation of an experimental design and comparison of motor outcome measure sensitivity to change*

period of corticospinal excitability that was increased above baseline. This will be a proof of principle trial to validate the methodology of this protocol.

2.3. *rTMS is a relatively new therapeutic modality that shows great promise in the treatment and evaluation of a variety of conditions and is already FDA-approved for the treatment of depression. However, various target stimulation parameters and protocols make comparison across research groups difficult, leading to a knowledge gap. Validating a systematic methodological approach in healthy people will allow comparison to previous work as well as establishing a baseline for moving forward to compare metaplasticity in brain disease states.*

3. Study Design

3.1. *This will be a randomized, sham-controlled, double blinded crossover trial in a healthy population.*

[figure not shown]

Figure 1: Subjects will enter the randomization at green diamond. Example shown for a subject following the red line through 3 interventions and another example shown in the blue line receiving a different order of interventions. They will be randomized to a three-visit crossover with a week separation between each visit. There will be four measures taken each visit (M1-M4), which will be approximately 10 minutes apart. Measures taken at each time point include: physiological measures (e.g. MEP), behavioral outcomes (e.g. reaction time) and exploratory outcomes. Study is completed at the end of visit 3 (red octagon). C tDCS=cathodal tDCS; A tDCS=anodal tDCS.

3.2. *Participants will be blinded to treatment group. A team investigator, off-line, will conduct the raw data analysis (e.g. MEP amplitude and CSP) and will be different than the investigator applying the noninvasive neurostimulation to the*

PROTOCOL TITLE: *Metaplasticity in the human motor cortex: validation of an experimental design and comparison of motor outcome measure sensitivity to change*

treatment group. This additional blinding of the data analysis will help to provide another protection against bias.

4. Inclusion and Exclusion Criteria

4.1. Individuals will be screened for eligibility by a study team member. The study team member will ask the potential participant a series of questions to determine whether or not they meet the inclusion/exclusion criteria.

4.2. Inclusion Criteria:

- a) Participant must be at least 18 years of age (all genders, races, and ethnicities)*
- b) Participant must have no current psychiatric or neurologic issues*
- c) Participant must not have any conditions listed in the exclusion criteria*
- d) Participant must be fluent in English*

Exclusion Criteria:

- a) History of major psychiatric illness*
- b) Actively using a neuropsychoactive medication*
- c) Legal or mental incompetency*
- d) Substance use disorder, abuse or dependence, with active use within the last 3 months*
- e) Significant medical or neurological illness*
- f) Prior neurosurgical procedure*
- g) History of seizure*
- h) History of ECT or TMS treatment within the past three months*
- i) Presence of a pacemaker, implanted medical pump or device, metal plate, or metal object in skull or eye (including shunts, dental implants, facial tattoos with metallic ink)*
- j) Pregnant women*

4.3. This study will not include any participants from any special populations (adults unable to consent, children, pregnant women, or prisoners).

4.4. This study will exclude pregnant women and children (due to safety and potential risk), prisoners and those who cannot competently provide their own consent (due to these groups being special populations) and will also exclude those who do not fluently speak or understand English (as our consent will be in English and study team members are fluent in English).

PROTOCOL TITLE: *Metaplasticity in the human motor cortex: validation of an experimental design and comparison of motor outcome measure sensitivity to change*

5. Number of Subjects

- 5.1. *This is not a multisite study and will only recruit subjects at this site.*
- 5.2. *We will aim to recruit 16 subjects for this study.*
- 5.3. *Sixteen subjects will be enrolled for this study according to the MANOVA model (anodal, cathodal, and sham) and a specified number of variables (time points—M1-M4) at the significance level of $\alpha=0.05$ and 80% power to correspond to the very large effect size. We have based the calculation on the very large effect size as seen in Quartarone et al., 2005. The desired sample size was found to be 16 patients per treatment arm. We will fulfill this sample size requirement with a crossover design as all 16 subjects will participate in each treatment arm. We would request a recruitment ceiling of 20 subjects to account for subject dropout and if a subject were to meet exclusion criteria after signing the consent.*

6. Study Timelines

- 6.1. *Study subjects will participate in three visits total. Each visit will consist of a visit length of 1 to 1 ½ hours in duration. The visits will be approximately one week apart. There will be no scheduled follow-up after the third subject visit. We anticipate that it will take 8 months to enroll all subjects. We expect to complete enrollment of all subjects and completion of experiments in 1 year. We expect data analysis and publication to occur within 2 years of study commencement.*

7. Study Endpoints

- 7.1. *The primary endpoint will be change in motor evoked potential (MEP) amplitude over the first dorsal interosseous (FDI) muscle of the dominant (right) hand pre- and post-intervention (tDCS and rTMS—time points M1-M3) as well as 10 minutes post intervention (time point M4). The secondary endpoint will be the comparison in an exploratory but systematic fashion various measures of motor cortex excitability (e.g. peak-to-peak amplitude change in motor evoked potential (MEP), the integrated area of the MEP (root mean square), the cortical silent period (CSP)), and behavioral measures (reaction time).*
- 7.2. *We will collect data on the safety of rTMS in this patient population including expected side effects: headache (expected 17% with transient headache that responds to simple analgesic) and nonspecific feelings of discomfort. We will collect data on rare but serious adverse events such as seizures (reported at 1.4%). No seizures have been reported in the literature on rTMS in the dystonia population thus far (Lefaucheur et al., 2014).*

8. Research Setting

- 8.1. *The study visits will all take place in the Noninvasive Neurostimulation Lab located on the 2nd floor of the Clinical and Translational Science Center (CTSC).*
- 8.2. *Potential subjects will be recruited and identified through the healthy participant registry through the CTSC as well as fliers placed throughout the Health Sciences Center and Main Campus.*

PROTOCOL TITLE: *Metaplasticity in the human motor cortex: validation of an experimental design and comparison of motor outcome measure sensitivity to change*

8.3. *Research procedures will be performed in the Noninvasive Neurostimulation Lab located on the 2nd floor of the CTSC. Analysis will be performed between the offices of [name], [name], and the CTSC Biostatistics core.*

8.4. *N/A*

8.5. *N/A*

9. Resources Available

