11.1. N/A

11.2. N/A

11.3. N/A

12. Study Procedures

12.1. *Visit 1: After informed consent, subjects will be seated in a comfortable chair. Surface EMG leads will be applied to clean and prepped skin over the right hand over the first dorsal interosseous muscle (FDI). The motor hotspot for FDI will be identified with TMS on the contralateral hemisphere. Resting motor threshold and active motor threshold will be determined.*

- **M1** (pre-tDCS measurement): neurophysiological outcome assessment (MEP, CSP) and behavioral outcome (reaction time task)
- **Priming Intervention** 10 min tDCS (cathodal, anodal or sham)
- **M2** (pre-tDCS measurement): neurophysiological outcome assessment (MEP, CSP) and behavioral outcome (reaction time task)
- **Inhibitory Intervention** 15 min rTMS over the dominant primary motor cortex at 1Hz
- **M3** (post-rTMS measurement): neurophysiological outcome assessment (MEP, CSP) and behavioral outcome (reaction time task)
- **M4** (10 minutes post-rTMS measurement): neurophysiological outcome assessment (MEP, CSP) and behavioral outcome (reaction time task)

PROTOCOL TITLE: *Metaplasticity in the human motor cortex: validation of an experimental design and comparison of motor outcome measure sensitivity to change*

Visit 2:

- **M1** (pre-tDCS measurement): neurophysiological outcome assessment (MEP, CSP) and behavioral outcome (reaction time task)
- **Priming Intervention** 10 min tDCS (cathodal, anodal or sham)
- **M2** (pre-tDCS measurement): neurophysiological outcome assessment (MEP, CSP) and behavioral outcome (reaction time task)
- **Inhibitory Intervention** 15 min rTMS over the dominant primary motor cortex at 1Hz
- **M3** (post-rTMS measurement): neurophysiological outcome assessment (MEP, CSP) and behavioral outcome (reaction time task)
- **M4** (10 minutes post-rTMS measurement): neurophysiological outcome assessment (MEP, CSP) and behavioral outcome (reaction time task)

Visit 3:

- **M1** (pre-tDCS measurement): neurophysiological outcome assessment (MEP, CSP) and behavioral outcome (reaction time task)
- **Priming Intervention** 10 min priming tDCS (cathodal, anodal or sham)
- **M2** (pre-tDCS measurement): neurophysiological outcome assessment (MEP, CSP) and behavioral outcome (reaction time task)
- **Inhibitory Intervention** 15 min rTMS over the dominant primary motor cortex at 1Hz
- **M3** (post-rTMS measurement): neurophysiological outcome assessment (MEP, CSP) and behavioral outcome (reaction time task)

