13.2. *Power analysis:* Sixteen subjects will be enrolled for this study according to the MANOVA model (anodal, cathodal, and sham) and a specified number of variables (time points—M1-M4) at the significance level of $\alpha=0.05$ and 80% power to correspond to the very large effect size. We have based the calculation on the very large effect size as seen in Quartarone et al., 2005. The desired sample size was found to be 16 patients per treatment arm. We will fulfill this sample size requirement through a crossover trial as all 16 subjects will participate in each treatment arm. We would request a recruitment ceiling of 20 subjects to account for subject dropout and if a subject were to meet exclusion criteria after signing the consent.

14. Provisions to Monitor the Data to Ensure the Safety of Subjects

14.1. The PIs will consist of the medical monitoring team for this study due to its minimal risk status.

14.2. We will collect data on the safety of rTMS including expected side effects: headache (expected 17% with transient headache that responds to simple analgesic) and nonspecific feelings of discomfort. We will collect data on rare but serious adverse events such as seizures (reported at 1.4%).

14.3. The safety data will be reviewed on an ongoing basis during enrollment and conduct of the study.

14.4. We plan to follow the most recent safety recommendations from expert consensus panels on rTMS.

14.5. We have no planned formal analysis of the safety data.

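### The order of cathodal, anodal and sham is randomized with no stated balancing, and the model has no visit term, so chance order imbalance among 16 participants is uncontrolled

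*Combined protocol and SAP*

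**What the plan says.** Section 3.1 describes the design in one sentence: "This will be a randomized, sham-controlled, double blinded crossover trial in a healthy population". The Figure 1 legend adds "They will be randomized to a three-visit crossover with a week separation between each visit" and follows one participant's path, with "another example shown in the blue line receiving a different order of interventions". Order therefore varies between participants, but the text does not say how many orders are used or how many participants get each.

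Section 12.1 leaves the condition open at every visit: "10 min tDCS (cathodal, anodal or sham" for Visits 1 and 2, and the same three alternatives for Visit 3. M1 is measured before tDCS at each visit.

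On numbers, 13.2 states "The desired sample size was found to be 16 patients per treatment arm" and 5.3 states "We will fulfill this sample size requirement with a crossover design as all 16 subjects will participate in each treatment arm". Both sections allow for replacements: "We would request a recruitment ceiling of 20 subjects to account for subject dropout".

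The analysis in 13.1 is a MANOVA on the three conditions and the time points M1-M4. No visit, sequence or carry-over term is named. The primary endpoint in 7.1 is change in MEP amplitude across M1-M4.

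**The concern.** In a crossover, an effect of visit (first, second or third session) stays out of the comparison of conditions if each condition falls equally often at each visit, or if the model includes visit. The plan provides for neither. With 16 participants and six possible orders, chance alone can put cathodal stimulation noticeably earlier or later, on average, than sham. If the response to stimulation changes from one session to the next, part of that change is then read as a difference between cathodal and sham. Hypothesis 1 rests on how cathodal priming changes the response to rTMS, so this is the contrast exposed. Visits 2 and 3 each follow a session of tDCS plus rTMS about a week earlier, and section 2.1 starts from the premise that prior activity can alter plasticity. A change in response across sessions is therefore a fair thing to guard against, although the documents do not show that one occurs.

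**Working it through.** **Inputs from the documents.** Three conditions, one per visit, three visits (3.1, 12.1); 16 participants (5.3, 13.2); ceiling 20 (5.3, 13.2). The plan's own figure, 16 per arm, cannot be reproduced because the effect size is described only as very large. It is taken as given.

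**Assumption.** Simple randomization means that each participant is drawn independently from the six orders. The plan does not say this is the scheme.

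**Imbalance, simple randomization.** Let D be the visit number of cathodal minus the visit number of sham. Over the six orders D takes the values 1, 1, 2, -1, -1, -2, so its mean is 0 and its variance is (4×1 + 2×4)/6 = 2. For the mean over 16 participants, SD = √(2/16) = 0.354 visits.

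**Imbalance, permuted blocks of six.** Two full blocks (12 people) contribute exactly zero. The last four people are drawn without replacement from six orders, so the variance of their sum is 4 × 2 × (6-4)/(6-1) = 3.2, and SD = √(3.2/16²) = 0.112. The largest possible sum is 3, so the maximum is 3/16 = 0.19. Each condition falls at each visit 2 × 2 = 4 times in the full blocks and 0 to 2 times in the remainder, which gives 4 to 6.

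| With 16 participants | Simple | Blocks of six |
|---|---|---|
| SD of mean D | 0.354 | 0.112 |
| 95th percentile of absolute mean D | 0.69 | 0.19 |
| Absolute mean D at least 0.5 | 19% | 0% |
| Some condition at some visit 2 or fewer, or 9 or more, times | 48% | 0% |
| At least one order never used | 30% | 0% |

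The percentages for simple randomization come from simulated allocations. The last one agrees with inclusion-exclusion: 6(5/6)¹⁶ - 15(4/6)¹⁶ + 20(3/6)¹⁶ = 0.3245 - 0.0228 + 0.0003 = 0.302.

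**From imbalance to bias.** With a linear drift of b per visit in the response, bias = b × mean D. The documents give no b, so two assumed values are shown, in SDs of the within-person cathodal-minus-sham difference:

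- b = 0.3: simple, SD of bias 0.354 × 0.3 = 0.11 and 95th percentile 0.69 × 0.3 = 0.21; blocks, 0.03 and 0.06.
- b = 0.5: simple, 0.18 and 0.34; blocks, 0.06 and 0.09.

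For scale, a paired t test with 16 people has 80% power at a difference of 0.75 SD. With b = 0 there is no bias under either scheme.

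**Type I error.** A paired t test without a visit term, simulated under simple randomization, rejected in 0.046 of trials at b = 0.3 and 0.053 at b = 0.5 (nominal 0.05). Under blocks the rates were 0.034 and 0.019, so the test is conservative. The reason shows at b = 0.5. The test's estimated variance is about (1 + 2b²)/16 = 1.5/16 = 0.094. Under blocks the true variance is 1/16 + 0.0125 × 0.25 = 0.066. A visit term removes the drift from the estimated variance.

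**Carry-over.** Over a full set of six orders, cathodal is preceded by nothing, anodal and sham one third of the time each, and sham by nothing, anodal and cathodal. With carry-over effects L, the raw contrast keeps (L_anodal + L_sham)/3 - (L_anodal + L_cathodal)/3 = (L_sham - L_cathodal)/3. Balance does not remove this.

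**The case against.** The strongest reply is that the text is silent on balancing and does not reject it. A reader might infer that the trial uses unrestricted randomization. The documents do not say so, and the drawing in Figure 1 is not available here. That stands: the figures for simple randomization show what is possible under the text as written, not what the sponsor will do.

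Second, M1 is re-measured at every visit and the endpoint in 7.1 is change, so a shift affecting M1-M4 equally cancels. That also stands. Only drift in the response relative to M1 matters for the primary endpoint. Practice on the reaction-time task concerns exploratory Aim 2.

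Third, a reader might infer from 12.1 that hotspot and threshold work happens at Visit 1 only, which would make that visit different in kind. The same list mentions EMG leads only under Visit 1, yet MEPs are recorded at all three. The entries for Visits 2 and 3 look abbreviated, so this asymmetry is not established.

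Fourth, a reader might infer that the planned test is invalid. It is not: over repeated randomizations the error rate holds. What remains is extra variance, and an unadjusted chance bias in the one allocation actually drawn.

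**Conclusion.** The point holds as a gap in both design and analysis: order is randomized, no balancing is stated, and the model has no visit term. Under assumed simple randomization the cathodal-minus-sham imbalance has SD 0.35 visits, about three times the 0.11 under permuted blocks of six. Whether this matters in practice depends on drift in the within-visit response, which the documents do not quantify; with no such drift there is no bias. Two benefits should not be claimed for balancing. It cannot be exact with 16 participants, because 16 is not a multiple of six, and it does not deal with unequal carry-over, for which the plan relies on the one-week gap. The change is worth making because it is nearly free and the balance cannot be added once orders have been assigned.

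**What to change.** In 3.1, state that participants are allocated from a concealed list in permuted blocks of the six orders, each order once per block, and that a participant who replaces a dropout takes the dropout's order. In 13.1, add visit as a factor, so that the gain from balance reaches the test instead of making it conservative.

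The cost is one list prepared before enrolment and two sentences of text, with no extra visits, staff or participants. The downsides are slight predictability at the end of a block, which concealing the list limits, and two degrees of freedom for a three-level visit factor. The target of 16 can stay, with each condition falling 4 to 6 times at each visit. If exact balance is wanted, 18 completers would give it within the ceiling of 20, leaving room for two replacements instead of four.

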- *A NeuroConn MR transcranial electrical stimulator belonging to the Clinical Core will be used. This is a CE-certified medical device for conducting non-invasive transcranial direct current stimulation (tDCS), alternating (tACS) or random noise (tRNS) current stimulation on subjects. Transcranial stimulation using weak electric currents over a period of several minutes is demonstrated to modify neuronal excitability and circuit function and can serve to promote brain recovery and repair.*

PROTOCOL TITLE: *Metaplasticity in the human motor cortex: validation of an experimental design and comparison of motor outcome measure sensitivity to change*

- *Although risk for seizure is minimal, in the event this occurs the PI ([name]) will be on hand to administer immediate first aid and the hospital code team would be activated.*
- *All members of our small study team are involved in the development of this protocol. Upon approval, we will meet regularly to ensure that our research protocol is being appropriately implemented. Furthermore, there will be at least two members of the research team available for participant visits, ensuring accountability and safety procedures are being met.*
- *The signed CTSC resources attachment will be uploaded on the CTSC Submission page in Click.*

10. Prior Approvals

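### The protocol describes blinding for participants and off-line analysis only; nothing visible masks the person who records MEP, CSP and reaction time after tDCS

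*Combined protocol and SAP*

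**What the plan says.** Section 3.1 gives the label: "This will be a randomized, sham-controlled, double blinded crossover trial in a healthy population".

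Section 3.2 describes two blinded functions. The first is the participant: "Participants will be blinded to treatment group". The second is the scoring of the recordings: "A team investigator, off-line, will conduct the raw data analysis (e.g. MEP amplitude and CSP"), by someone who "will be different than the investigator applying the noninvasive neurostimulation". The section describes the purpose of that second layer this way: "This additional blinding of the data analysis will help to provide another protection against bias".

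Section 7.1 sets the primary endpoint: "The primary endpoint will be change in motor evoked potential (MEP) amplitude over the first dorsal interosseous (FDI) muscle", measured across M1 to M4. CSP and reaction time belong to the secondary endpoint, which the protocol treats as exploratory.

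Section 12.1 lists, for each of the three visits, M1, 10 minutes of tDCS (cathodal, anodal or sham), M2, 15 minutes of 1 Hz rTMS, M3 and M4. It names nobody as the person taking the measurements. (M2 is labelled pre-tDCS in that list, but it comes after tDCS there, and section 1.1 also places it directly after tDCS.)

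On staffing, section 9.3 says that "there will be at least two members of the research team available for participant visits".

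**The concern.** A recorded MEP depends on more than the cortex. Coil position and angle, how relaxed the hand is, and which sweeps are accepted all shape the trace as it is made. CSP depends on the contraction the participant is coached to hold, and reaction time on how the task is introduced and encouraged. An analyst who does not know the condition will measure faithfully whatever was recorded, including any shift introduced at that stage.

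Hypothesis 1 has a direction: cathodal priming is expected to reverse the inhibition that 1 Hz rTMS normally produces. An acquirer who knows which tDCS was given therefore knows which way the MEP is expected to move. The same team may see each participant under all three conditions. The aim is to validate a method for later use in patients, so a bias at acquisition could be carried into that later work.

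**Working it through.** **Step 1. Set the blinding text against the steps of a visit.**

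| Step | Where described | Stated protection |
|---|---|---|
| Participant receives tDCS | 3.2, 12.1 | Participant blinded |
| Operator sets cathodal, anodal or sham | 12.1 | None stated |
| MEP, CSP and reaction time recorded at M2 to M4 | 12.1 | None stated; no assessor named |
| Off-line scoring (examples given: MEP amplitude, CSP) | 3.2 | Different person from the stimulator; called blinded |
| Coding of files before scoring | Not described | None stated |

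Three things follow. First, the plan can be followed to the letter with one person giving tDCS and then recording the outcomes. Second, the analyst's blinding rests on being a different person, since no removal of condition labels from the files is described. Third, reaction time is not among the examples of what is scored off-line.

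The 1 Hz rTMS is listed identically at every visit, so the 10-minute tDCS is the only step that differs by condition and the only one that needs hiding.

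**Step 2. Is there a figure in the plan to reproduce?** None concerns blinding. Sections 5.3 and 13.2 give 16 subjects, alpha 0.05 and 80% power, which supply the n and alpha used below.

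**Step 3. How much could a shift at acquisition matter?** Suppose there is no true difference between two conditions, but acquisition adds a systematic shift of b standard deviations of the within-person difference. For a paired t test:

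- Degrees of freedom: n − 1 = 16 − 1 = 15.
- Two-sided 5% critical value: t = 2.131. Sidedness is my assumption, because the protocol does not state it.
- Noncentrality: b × √n = b × √16 = 4b.
- Rejection probability: P(T > 2.131) + P(T < −2.131), where T is noncentral t with 15 df and noncentrality 4b.

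| Assumed b | Noncentrality | Rejection probability |
|---|---|---|
| 0 | 0 | 5.0% |
| 0.10 | 0.4 | 6.6% |
| 0.25 | 1.0 | 15.5% |
| 0.50 | 2.0 | 46.5% |

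The values of b are assumptions. The documents give no SD and nothing from which a shift could be estimated. Section 13.1 plans a MANOVA over three conditions and M1 to M4, so this table shows how sensitive a 16-person comparison is; it does not give the error rate of the planned analysis.

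**The case against.** **Double blind may already cover the acquirer.** Section 3.2 calls the analyst measure additional, which can mean a layer on top of a blind that already includes the operator. The label can also mean participant plus analyst. Both readings are fair. A reader might infer that the operator is known to be unblinded, or that 3.1 and 3.2 contradict each other; the documents support neither. The label is ambiguous and the text is silent. What stands is that nothing visible requires the acquirer to be masked.

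**A role assignment may exist elsewhere.** The opening of section 9 (Resources Available) was not in the text reviewed, so this cannot be excluded. Sections 3 and 12, where it would be expected, contain none.

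**There are real protections.** Off-line scoring by a different investigator limits bias in reading MEP and CSP. Section 9.3 lists overhead coil holders and an optional chin-rest and neck brace, which would reduce variation in coil handling. Their use is not required, however, and they do not govern muscle state, instructions or sweep acceptance.

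**Staffing.** A reader might infer that the two people in 9.3 make the split free of any burden. The section gives their purpose as accountability and safety. One may be the PI, who is on site for quality control (16.7) and on hand in case of a seizure (9.3). Use of the TMS device is limited to the PI and staff she trains (33.1). The split fits the stated head count, but the documents do not show that both people are trained for it.

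**The numbers say nothing specific to this trial.** Correct: any 16-person paired test gives the same table.

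**Conclusion.** The gap is real. As visible, the plan protects the participant and the off-line scoring, and leaves the recording of the primary MEP endpoint, and of the exploratory CSP and reaction time, open to an acquirer who can know the tDCS condition. Off-line scoring cannot repair a shift already in the trace.

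The size of any bias is unknown. The 6.6%, 15.5% and 46.5% figures depend on the assumed shifts and on a single paired contrast that is not the planned test. They should not be read as expected false-positive rates. Nor does the protocol name a cathodal-versus-sham difference as its primary contrast: it compares pre- and post-measures across all three conditions. The point rests on Hypothesis 1 being directional, not on any particular contrast.

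This is a risk left open by silence, not a documented bias. It is worth closing because the remedy is cheap.

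**What to change.** In section 3.2, state blinding by role:

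1. Of the at least two team members available at each visit, one holds the allocation and sets up and removes tDCS.
2. The other stays unaware of the condition, away or screened during tDCS, and does the coil positioning, test pulses, CSP and reaction-time instructions and sweep acceptance at M1 to M4.
3. The off-line analyst receives files coded without condition.

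The cost is a paragraph and a role sheet, a hand-over around the 10-minute tDCS period, and making sure that the masked member is trained on the TMS device as 33.1 requires. No dose, schedule or sample size changes. If the site already works this way, it only needs to be written down.

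If the roles cannot be split, still code the files, describe the trial in 3.1 as participant- and analyst-blinded, and report unmasked acquisition as a limitation. That makes the description accurate but does not remove the risk, so the role split is the better choice.
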